# 6.2 Allowed and prohibited therapy

# 6.2.1 Allowed prior and concomitant therapy

All concomitant therapies except for those stated in Section 6.2.2 are allowed.

# 6.2.2 **Prohibited prior and concomitant therapy**

The drugs listed below are prohibited for use throughout the trial period:

- 1. Topical drugs (aerosols, sprays, inhalations, gargle solutions, fast-disintegrating tablets/lozenges/pastilles) in the pharynx or nose.
- 2. Systemic, inhalation, or nasal glucocorticosteroids.
- 3. Systemic or topical (intranasal or pharyngeal) antibacterial drugs.
- 4. Anti-viral drugs.
- 5. Immunomodulatory agents.
- 6. Painkillers or antipyretic agents.
- 7. Class I antiarrhythmics.
- 8. Cholinesterase inhibitors (including neostigmine, distigmine, pyridostigmine) and other drugs for myasthenia.

#### 6.3 Methods to monitor the subjects' compliance with trial procedures

At every visit after Visit 1, the subjects' compliance will be checked by counting the unused drug and analysis of the patient's diaries. It should be noted that the drugs doses stipulated by the protocol are 6 to 10 (maximum) lozenges per day (Angal),

and to 6 lozenges per day with at least 2-hour interval (ANTI-ANGIN® FORMULA). The both drugs should be taken when needed (a sore throat).

In view of the nature of drug intake (when needed), the lower margin of compliance will not be evaluated; the number of used lozenges is compared to maximum amounts stated in the protocol for the study drug (up to 10 lozenges per day for Angal) or Prescribing Information for the comparator drug (up to 6 lozenges per day for ANTI-ANGIN® FORMULA).

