• Measurement of the main vital signs;
• Hematology;
• Biochemistry;
• Urine pregnancy test;
• 12-lead ECG;
• Evaluation of inclusion/non-inclusion criteria;
Randomization;
• Dispensing of the study drugs;
• Provision with the patient's diaries and training on the fill-in rules;
• Initiation of therapy with the study drugs;

• Evaluation of adverse events (including based on results of the throat and pharynx examination).
After the screening tests completion, on the same day, the patients who meet all the inclusion criteria will be randomized into one of the two trial groups (arms): Angal or ANTI-ANGIN ® FORMULA. Therapy group will be assigned by randomization (in 1:1 ratio). The patients will be given the relevant study drugs and the patient's diaries.
The first use of the drug corresponding to the assigned therapy group on Day 1 after randomization will be considered to be the treatment initiation (for the both groups). The patients will be instructed on how to fill in the patient's diaries.
Group A, therapy with Angal:
1 lozenge with a not less than 2-hour interval, up to 6–10 times per day, for 4 days or until full recovery (whichever occurs first during 4 days of therapy). A single dose of Angal is 1 lozenge. The lozenges are intended for full dissolution in the oral cavity. One lozenge is slowly disintegrating in the mouth.
Group B, therapy with ANTI-ANGIN ® FORMULA
1 lozenge with a not less than 2-hour interval, up to 6 lozenges per day, for 5 days or until full recovery (whichever occurs first during 5 days of therapy). One dose of ANTI-ANGIN ® FORMULA is 1 lozenge. The lozenges are intended for full dissolution in the oral cavity. One lozenge is slowly disintegrating in the mouth.
Visits during therapy with Angal or ANTI-ANGIN ® FORMULA
During Days 2 and 3 of the therapy, the patients (in the both groups) do not visit the trial site.
In case of worsening, including signs of the secondary bacterial infection, the patients must inform the Investigator who may decide on early discontinuation of the study drug. In this case, an unscheduled visit to the trial site is required.

Visit 2 (Day 4):
Visit 2 is conducted on Day 4; the patient must visit the trial site in the fasted state and bring the filled-in diary and unused drug.

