#### 4.2.3.2.3 Fill-in of TSS questionnaire

TSS, a questionnaire (point scale) for healthcare professionals, is used in clinical practice as well as clinical trials to evaluate dynamic changes of symptoms severity of the infection-inflammatory process in the throat (Bereznoy VV, Riley DS, Wassmer G, Heger M. Efficacy of extract of Pelargonium sidoides in children with acute non-group A beta-hemolytic streptococcus tonsillopharyngitis: a randomized, double-blind, placebo-controlled trial). One of such clinical trials with TSS questionnaire was conducted in 2005 in Germany, ©CRO Applertee AG. A version of TSS ©CRO Applertee AG was adapted for this protocol.

TSS (Tonsillopharyngitis Severity Score) is a questionnaire for evaluation of the following symptoms severity: pharyngalgia, difficulty in swallowing, salivation, hyperemia of pharyngeal mucosa, and body temperature increase according to a 4-point scale:

- 0 = no symptom;
- 1 = insignificant symptom;
- 2 = moderate symptom;
- 3 = significant symptom.

The axillary body temperature increase is rated as follows:

- 0 points: <37.5 °C;
- 1 point: 37.5 to <38.5 °C;
- 2 points: 38.5 to <39.5 °C;
- 3 points: >39.5 °C.

TSS is filled in by the Investigator based on the patient complaints and physical examination data. The Investigator summarizes the points obtained for every symptom to obtain a total sum of TSS points. A total sum of TSS points will be used at screening to evaluate for a subject's eligibility and baseline evaluation; at Visit 2 (Day 4), to measure efficacy of the trial therapy in the both groups; to evaluate the disease outcomes on Visit 2 (Day 4) and/or Visit 3 (Day 5), where applicable.

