# 1 Introduction

This trial has been designed and conducted to evaluate the therapeutic efficacy and safety of the study drug Angal, lozenges [menthol], 1.0 mg + 5.0 mg (Sandoz d.d., Slovenia), comparing to ANTI-ANGIN® FORMULA, lozenges, 0.2 mg + 2.0 mg + 50 mg (OOO Valeant, Russia), in the treatment of patients with uncomplicated acute infectious and inflammatory diseases of the pharynx accompanied by a sore throat. The objective of this Phase III trial is to demonstrate the non-inferior therapeutic efficacy of the study drug as compared to the reference product.

This Statistical Analysis Plan was developed in accordance with the following documents:

- Guidelines for examination of medicinal products, Vol. 1. Federal State Budgetary Institution Scientific Center for Expert Evaluation of Medicinal Products under the Ministry of Health of the Russian Federation (eds. A.N. Mironov). Moscow: Grif and K, 2013.
- ICH harmonised tripartite guideline. Statistical principles for clinical trials (E9). Current Step 4 version dated 5 February 1998.
- GCP rules of the Eurasian Economic Union (a draft).

The objective of this Statistical Analysis Plan is more detailed, compared to Section 9 of the trial protocol, description of the main principles of the protocol-based statistical analysis, description of the primary and secondary endpoints analysis methods, as well as other data obtained during the trial.

This Plan stipulates for consistence of the scheduled and conducted statistical analysis to the trial protocol, including definition of the analysis data sets, transformations and calculations for the endpoints, observations quantity needed, etc. No changes in this Statistical Analysis Plan compared to the trial protocol are envisaged.

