## 3 Main provisions for analysis

## 3.1 Study drugs and therapy schedule

The patients were randomized in 1:1 ratio to the following groups:

**Main group:** Angal, lozenges [Menthol], 1 mg + 5 mg (Sandoz d.d., Slovenia): Administration of 1 lozenge with a not less than 2-hour interval until full dissolution in the mouth, up to 6–10 times per day, for 4 days or until full recovery (whichever occurs first during 4 days of therapy).

**Control group:** ANTI-ANGIN® FORMULA, lozenges, 0.2 mg + 2 mg + 50 mg (OOO Valeant, Russia): administration of 1 lozenge with a not less than 2-hour interval, up to 6 lozenges per day, for 5 days or until full recovery (total TSS  $\leq 2$ ) (whichever occurs first during 5 days of therapy).

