## **3.2** Serious protocol deviations

A serious protocol deviation (Item 11.3 of the trial protocol) is a deviation, which may, according to the estimate by the Investigator or a person assigned by the Investigator, result into withdrawal of the subject from the trial or withdrawal of his data from the statistical part of the trial. The deviations not referred to as serious ones shall be considered minor protocol deviations.

For the purposes of this analysis, the serious protocol deviations were defined as follows:

Description	Example/Explanation	Efficacy or safety	Excluded from population:
inclusion and non-	Inclusion criterion No. 5: e.g., inclusion of the patient with initial total TSS $< 5$	Efficiency	РР
Violation of the informed consent receipt procedure	Absence of the Informed Consent Form	Safety and efficacy	All

	Informed Consent Form was signed after randomization/initiation of therapy	Safety and efficacy	None
Randomization and study drugs	Prescription of the drug non-consitent with the randomization arm	Efficiency	РР
	Low compliance: the patient missed more than 3 doses of the study drug	Efficiency	РР
Concomitant drugs	The patient used prohibited drugs during the trial (or had used the drugs prohibited by the inclusion/exclusion criteria before the trial initiation)	Efficacy and safety	РР

A final list of serious protocol deviations will be compiled before the statistical analysis start. Every protocol deviation should be evaluated for the patient's exclusion from the PP data set or statistical analysis by the trial Sponsor representative. The decisions adopted and lists of patients included into the relevant data sets must be documented before the analysis initiation.

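### SAP 3.2 drops patients from the PP set for missing more than three doses, but Protocol 6.3 makes dosing as-needed and declines to assess low use, so a missed dose has no agreed reference

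*Protocol*

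**What the plan says.** Protocol 6.3 describes intake in both arms as symptom-driven: "The both drugs should be taken when needed (a sore throat". It draws the consequence for compliance directly: "In view of the nature of drug intake (when needed), the lower margin of compliance will not be evaluated". What remains is a check against the ceiling: "the number of used lozenges is compared to maximum amounts stated in the protocol for the study drug", with the same check for the comparator. The ceilings are 10 Angal and 6 ANTI-ANGIN FORMULA lozenges a day.

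The regimens fit that reading. SAP 3.1 gives Angal as "up to 6–10 times per day, for 4 days or until full recovery (whichever occurs first during 4 days of therapy". The comparator is limited to 6 a day for up to 5 days, also ending at recovery. Protocol 4.4.4 and 6.1 define recovery as total TSS of 2 or less.

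In its table of serious deviations, SAP 3.2 includes "Low compliance: the patient missed more than 3 doses of the study drug" and marks it as excluding the patient from PP. It does not say what counts as a missed dose or over which days to count. SAP 1 states: "No changes in this Statistical Analysis Plan compared to the trial protocol are envisaged". SAP 3.3 and 4.1.2 make ITT the main analysis of the primary endpoint and PP the additional one.

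**The concern.** A rule that penalises too few doses is a lower margin of compliance, which Protocol 6.3 says will not be assessed. SAP 1 rules out reading it as a declared change.

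The consequence falls on PP, the supporting analysis of the primary endpoint in a non-inferiority trial. With as-needed dosing, use can fall because the throat is getting better. A patient who tapers for that reason follows Protocol 6.3 but could be classed as a serious deviator, so PP membership would then depend partly on a consequence of response. If the daily maxima served as the reference, the hurdle would also differ between arms, because one maximum is 10 and the other 6. The trial is open-label (Protocol 4.3.2), and a Sponsor representative judges each case.

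**Working it through.** The plan gives no number of due doses to reproduce, so the check compares the texts and then shows how far the result moves with the reference chosen.

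**1. Is there a reference for 'missed'?**
- Comparator: only a maximum of 6 a day (Protocol 6.1, 6.3; SAP 3.1). No minimum appears.
- Angal: Protocol 6.3 and the dosage text in 2.1.1 mention 6 to 10 a day, which could be read as a floor of 6. Against that, Protocol 6.1 gives the dose as needed and as an upper limit, and 6.3 declines to assess a lower margin.
- Stopping at recovery does not settle it. "TSS is filled in by the Investigator based on the patient complaints and physical examination data", and "During Days 2 and 3 of the therapy, the patients (in the both groups) do not visit the trial site". Unless there is an unscheduled visit, the day on which TSS reached 2 or less is not recorded on Days 2–3.
- Window: none in SAP 3.2.

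**2. Spread under assumed references.** Due = assumed daily number × days. More than 3 missed means 4 or more, so staying in PP needs at least due − 3. Days 1–3 is my choice of window, being the period before the Day 4 assessment.

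| Assumed reference | Due | Needed to stay in PP |
|---|---|---|
| Angal, 10/day, Days 1–3 | 3 × 10 = 30 | 27 (90%, mean 9/day) |
| Angal, 6/day, Days 1–3 | 3 × 6 = 18 | 15 (83%, mean 5/day) |
| Comparator, 6/day, Days 1–3 | 3 × 6 = 18 | 15 (83%, mean 5/day) |
| Angal, 10/day, 4 days | 4 × 10 = 40 | 37 (92.5%) |
| Angal, 6/day, 4 days | 4 × 6 = 24 | 21 (87.5%) |
| Comparator, 6/day, 5 days | 5 × 6 = 30 | 27 (90%) |
| Protocol 6.3 as written | none | nobody can deviate |

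**3. Angal at constant use, Days 1–3.** Taking 6, 7, 8, 9 or 10 a day gives 18, 21, 24, 27 or 30 lozenges. Against 30 due, the missed counts are 12, 9, 6, 3 and 0, so 6, 7 or 8 a day is a deviation. Against 18 due, none of these patients misses any. Over 4 days, 6 a day (24 lozenges) is 0 missed against 24 or 16 against 40.

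**4. A patient tapering as pain eases.** Use of 6, 5, 3 gives 14 lozenges. In the comparator arm, 18 − 14 = 4 missed against the maximum, a deviation. In the Angal arm the same use is also 4 missed against a floor of 6 a day, and 30 − 14 = 16 against the maximum. Under Protocol 6.3 both patients comply.

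**5. By arm.** With the maxima as reference over Days 1–3, staying in PP needs 90% of the reference on Angal and 83% on the comparator.

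**The case against.** The best defence is that the row is not an automatic count. It sits in a column of examples and explanations. SAP 3.2 says a final list of serious deviations will be compiled before the analysis, that each deviation will be evaluated individually, and that decisions and patient lists will be documented beforehand. This stands, and it means a reader should not infer that the rule is impossible to operate. What the review lacks is a criterion.

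The diary helps as well. Three times a day it asks whether the patient is well enough to do without lozenges, and it logs the time of each lozenge and whether pain was present. A careful review could often tell improvement from neglect. But the item is the patient's own judgement rather than TSS of 2 or less, it yields no due-dose count, and SAP 3.2 does not refer to it.

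A reader might also infer that no due-dose figure exists in either arm. That is too strong for Angal, where a floor of 6 a day can be argued, and under it every constant use from 6 to 10 a day passes. The figures against 10 a day rest on a reference that no document adopts. The comparator has no floor at all.

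Protocol 5.3.1 does list non-compliance as a ground for exclusion from the trial. It sets no threshold and does not displace the specific statement in 6.3.

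Finally, under-exposure in both arms can pull them together in a non-inferiority trial, so a minimum-exposure rule has a legitimate purpose. That is an argument for writing one into the protocol, which 6.3 deliberately does not do.

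**Conclusion.** SAP 3.2 contradicts Protocol 6.3 on low use, and SAP 1 denies any change. Within the conflict, 'missed more than 3' has no agreed reference or window. Depending on the assumption, the row removes nobody (6.3 as written) or everyone short of 83% to 92.5% of an assumed number. It could remove patients who comply with 6.3 and use fewer lozenges because they are improving, and it would act differently by arm if the maxima were the reference.

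The size of the effect on PP cannot be derived, because the documents give no distribution of lozenge use. A reader might infer that PP would be biased towards Angal or that the non-inferiority conclusion is at risk. The documents do not support either: improving patients could leave PP in both arms, the direction of any shift in the difference is unknown, and the main ITT analysis does not use this rule. The row should be corrected before the PP list is fixed, but it does not threaten the main result.

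**What to change.** Delete the low-compliance row from SAP 3.2, and keep it out of the final deviation list, so that PP follows Protocol 6.3. Define the compliance figure in SAP Table 24, whose template gives no formula, as lozenges used per day by arm, for description only and with no exclusion attached. Do not replace the row with a PP exclusion for exceeding the maximum on a single day: Protocol 6.3 compares use with the maximum but attaches no such exclusion, and one extra lozenge would then remove a patient.

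The cost is one deleted row and one table definition in the SAP. No protocol amendment is needed, because the change restores the protocol's rule. No new data are needed, because the diary and the count of unused lozenges already record use. ITT and the sample size are unchanged. The downside is that PP then carries no explicit minimum-exposure criterion, so a patient who took very few lozenges could remain in it; Protocol 6.3 already intends this, and the descriptive table would show how common it is.

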# 7 Efficacy evaluation

#### 7.1 List of efficacy parameters

#### Primary outcome measure

The primary outcome measure was the percentage of patients without sore throat after 3 days of therapy on Day 4, as evaluated by the Investigator according to the Tonsillopharyngitis Severity Score (TSS), in both Angal and ANTI-ANGIN® FORMULA arms.

#### Secondary outcome measures

The secondary outcome measures in the both therapy groups were:

- The frequency of ≥50% total score reduction according to the TSS questionnaire completed by the Investigator as compared to the baseline in both Angal and ANTI-ANGIN® FORMULA groups at Visit 2 (Day 4).
- Total score reduction according to the TSS questionnaire, as well as a reduction in the symptoms (sore throat, difficulty in swallowing, salivation, erythema, and fever) after a 3-day therapy, at Visit 2 (Day 4), as compared to the baseline total score.
- A period of time required for disease symptoms relief, determined according to the patient's diary (subjective patient's evaluation), but no more than 5 days during the trial—for patients who have achieved the corresponding outcome.
- A proportion (%) of patients who fully recovered by Day 4 in Group A and by Day 5 in Group B (the outcome of a disease according to the objective evaluation by the Investigator, the total score according to the TSS questionnaire ≤2).
- A change in the sore throat intensity by 100 mm VAS (visual analogue scale filled in by the patient) at the beginning, after 3 days of therapy, and at the end of treatment in both groups.

#### 7.2 Methods and timing for evaluation, recording, and analysis of efficacy parameters

The methods for efficacy criteria evaluation are described in Section 4.2.3.2. The first endpoint is evaluated in the morning at Visit 2 (Day 4, after 3 days of the trial therapy) before the study drugs intake. Other efficacy endpoints are evaluated in terms stated in Section 7.1.

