# 4.2.4.2 Efficacy evaluation visit (Visit 2, Day 4)

Visit 2 is conducted on Day 4; the patient must visit the trial site in the fasted state and bring the filled-in diary and unused drug.

If Group B patients (ANTI-ANGIN® FORMULA) did not meet recovery criteria (total  $TSS \le 2$ ) at Visit 2 (Day 4), they will require continuation of the therapy, and some procedures for those patients will be transferred for the next day (Visit 3, Day 5), see below. The patients will keep their diaries and the unused drugs.

Visit 2 procedures for the both groups:

- Collection of complaints, actualization of anamnesis;
- Records on the concomitant therapy;
- Physical examination (including oropharynx);
- Measurement of the main vital signs;
- Evaluation of adverse events (including based on results of the throat and pharynx examination);
- Evaluation of exclusion criteria;
- Compliance evaluation (diary completion, administration of the study drugs).

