#### 4.2.4.6 Visit of premature discontinuation of the trial

Visit 2 procedures will be applied for the visit of premature discontinuation.

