#### 9.5 Accounting for missed, unanalyzable, and questionable data

During the monitoring visits to the trial sites, the clinical trial specialists (monitors) authorized by the Sponsor will analyze eCRFs for the data completeness. In the case of absence of data on CRFs and availability of relevant information in the primary documentation, questions for investigators and regulations to address inconsistencies will be formulated. At the database check, the expert in statistics authorized by the Sponsor and the data control and processing managers will analyze the trial results for questionable, missed, and unanalyzable data, which might be the basis for the questions for investigators. If possible, the investigators will eliminate the errors identified in CRFs and inform the Principal Investigator and authorized representatives of the Sponsor hereof. In case the identified data errors cannot be eliminated after the completion of the patients participation in the trial, an analysis of the resulting parameter sensitivity to questionable data will be conducted in the statistical analysis.

Information about the missed, questionable, and unanalyzable data will be summarized in the final clinical trial report.

The main analysis for the primary endpoint will be conducted without replacement for the missed, questionable, or unanalyzable data. An additional analysis will be conducted with the data replacement (last observation carried forward); in this case, the last known TSS score will be carried to all subsequent control points.

All other data will be analyzed based on actually available information only, without data replacement.

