#### 9.7 Selection of subjects for analysis

The following data sets will be used for analysis:

• The intention-to-treat (ITT) population: all randomized subjects who have received at least one dose of the study drug/placebo and have completed at least one visit aimed at evaluation of the efficacy parameters (i.e., at least all the procedures of Visit 1).

According to the ICH E9 requirements, the ITT population will be considered to be a population for statistical analysis in the equivalence trials (including non-inferiority trials).

- The per protocol (PP) population: all randomized subjects who have completed participation in the trial in accordance with the protocol (have completed the prescribed period of treatment and follow-up without significant deviations from the protocol).
- The safety population (safety): all randomized subjects who received at least one dose of the trial/reference drug and have completed at least one visit to the evaluation of the parameters of safety (i.e., at least all the procedures of Visit 1). As distinct from ITT population, the safety population will be analyzed depending on actually received treatment (not only prescribed) (in case of difference between the prescribed and received therapies).

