## 3.6 Missed data and outliers

At the database check, the expert in statistics authorized by the Sponsor and the data control and processing managers will analyze the trial results for questionable, missed and unanalyzable data, which will be the basis for the questions for investigators.

If possible, the investigators will eliminate the errors identified in CRFs and inform the Principal Investigator and authorized representatives of the Sponsor hereof. In case the identified data errors cannot be eliminated after the completion of the patients participation in the trial, the analysis of the resulting parameter sensitivity to questionable data will be conducted in the statistical analysis.

Information about the missed, questionable, and unanalyzable data will be summarized in the final clinical trial report.

The main analysis for the primary endpoint will be conducted without replacement for the missed, questionable, or unanalyzable data.

An additional analysis will be conducted with the data replacement (last observation carried forward); in this case, the last known TSS score will be carried to all subsequent control points.

All other data will be analyzed based on actually available information only, without data replacement.

Regarding abnormal test results, their clinical significance is evaluated by the Investigator during the trial with registration of AEs or adverse reactions, under control of the clinical trial specialists. Additional inquiries may be forwarded to the trial sites (before the cut-off date) if clinical significance of the abnormal test results is hard to evaluate.

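### No rule says how a banned-painkiller user's Day 4 score counts in the ITT main analysis, so a recorded 0 is a success on a pain endpoint

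*Protocol*

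**What the plan says.** **Endpoint and timing.** The primary outcome is the Investigator-rated absence of sore throat on the TSS at Day 4. Protocol 7.2 says it is "evaluated in the morning at Visit 2 (Day 4, after 3 days of the trial therapy) before the study drugs intake". That is the only timing condition. The advice in Protocol 4.2.3.2.4 to score before painkillers where possible concerns the VAS, not the TSS.

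**Rules on painkillers.** Protocol 6.2.2 bans painkillers throughout. Protocol 5.3.1, item 11, requires exclusion of a patient who receives or needs additional therapy that could affect the results. Protocol 5.2, item 4, bars entry after an analgesic in the preceding 12 hours.

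**When use comes to light.** The synopsis states: "During Days 2 and 3 of the therapy, the patients (in the both groups) do not visit the trial site". The diary (Appendix 3) asks about lozenges, temperature and course of disease, and has no field for other medicines. The next scheduled collection is at Visit 2, where the procedures include "Records on the concomitant therapy" and where Table 1 also places the TSS. For early withdrawal, Protocol 4.2.4.6 says: "Visit 2 procedures will be applied for the visit of premature discontinuation".

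**Analysis sets and missing data.**
- SAP 3.2 lists "The patient used prohibited drugs during the trial" as a serious deviation, with removal from PP only. A Sponsor representative also assesses each deviation for exclusion before the analysis.
- ITT is "all randomized subjects who have received at least one dose of the study drug/placebo" and who completed the Visit 1 procedures (Protocol 9.7). ITT is the main analysis and PP the additional one.
- Protocol 9.5: "The main analysis for the primary endpoint will be conducted without replacement for the missed, questionable, or unanalyzable data". In the additional LOCF analysis, SAP 3.6 says "the last known TSS score will be carried to all subsequent control points".

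**The concern.** The endpoint is pain, and a painkiller acts on it directly. The protocol recognises this at entry with its 12-hour limit, but has no counterpart for the Day 4 TSS when the ban is broken.

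Use at home on Days 2 and 3 will often first be recorded at Visit 2, the visit at which the primary score is taken. Withdrawing the patient then does not remove the score. The patient stays in ITT, the score is used as recorded, and a 0 is a success. PP drops the patient, and LOCF also takes the score without regard to painkillers. The need for a painkiller is nowhere treated as a failure of the lozenge.

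In a non-inferiority comparison this does not require imbalance between arms. If the same share of failures is masked in each arm, the arm with more failures gains more apparent successes, and the difference moves toward zero.

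**Working it through.** **Inputs.** Comparator rate 63%, Angal rate 65%, margin 14.5 points, 10% discontinuation and 140 randomized per arm (Protocol 9.2); Newcombe interval, two-sided 90% (Protocol 9.1.2, SAP 4.1.2). Assumed here: 140 × 0.9 = 126 evaluable per arm, non-inferiority declared when the lower limit is above −14.5 points, and every masking or reclassification share below.

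**The plan's own figure.** The plan states 128 per arm for 80% power at one-sided 2.5%. Exact binomial enumeration with the Newcombe interval gives 79.2% power at 128 and first reaches 80% at 131, which agrees within 3%. The standard unpooled closed formula gives 133. All further results use the 90% CI rule, exact binomial sums and 126 per arm.

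**Masking at the margin.** Let the true rates be 48.5% and 63%, and let a share m of failures in each arm be scored 0 after a painkiller.
- Angal: 48.5 + 51.5m. Comparator: 63 + 37m. Difference: −14.5(1 − m).

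| m | Angal % | Comparator % | Difference | Masked patients (Angal, comparator) | False non-inferiority |
|---|---|---|---|---|---|
| 0 | 48.50 | 63.00 | −14.50 | 0, 0 | 5.13% |
| 5% | 51.08 | 64.85 | −13.78 | about 3, 2 | 6.39% |
| 10% | 53.65 | 66.70 | −13.05 | about 6, 5 | 7.96% |
| 20% | 58.80 | 70.40 | −11.60 | about 13, 9 | 12.77% |

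Dropping the masked patients, as PP does, gives 5.35% at m = 10% (120 vs 121 patients) and 6.31% at m = 20% (113 vs 117).

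**Results near plan.** Lower limits with 126 per arm: 82 vs 79 successes, −7.51; 79 vs 79, −9.93; 74 vs 79, −13.93; 73 vs 79, −14.72. Reversal needs a net 82 − 73 = 9 masked Angal patients in the first case and 79 − 73 = 6 in the second.

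**Counting users as failures.** Suppose a share r of successes in each arm used a painkiller but would have been pain-free anyway. Each rate is multiplied by (1 − r), so at the margin the difference becomes −14.5(1 − r).

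| r | Pass rate at the margin | Power at 65% vs 63% |
|---|---|---|
| 0 | 5.1% | 86.5% |
| 2% | 5.7% | 85.8% |
| 5% | 6.6% | 84.9% |
| 10% | 8.2% | 83.9% |

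**Whether the counting rule can matter.** A constructed example with 10 Angal and 5 comparator users among 128 per arm, all scored 0: counted as successes (80/128 vs 81/128) the 90% lower limit is −10.6; dropped (70/118 vs 76/123), −12.7; counted as failures (70/128 vs 76/128), −14.7. Only the last misses the margin. These counts are invented to show sensitivity and are not a forecast.

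**The case against.** **There are rules for painkiller users.** A reader might infer that the plan has none. It does: the ban, mandatory withdrawal, removal from PP, and a documented Sponsor assessment of each deviation before analysis. This objection stands and limits the point to the ITT main analysis. The Sponsor assessment does not fill that gap, because it can only exclude a patient; it cannot count one as a failure. The sensitivity analysis in Protocol 9.5 does not fill it either: it covers data errors that cannot be resolved, and a correctly recorded score is not an error.

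**Not every user ends up with a Day 4 score.** Worsening must be reported and leads to an unscheduled visit, so some users will be withdrawn earlier. Nothing says whether a score taken at the discontinuation visit stands for Day 4. This is correct: the claim covers users who have a recorded Day 4 score. A user without one drops out unreplaced, again not as a failure.

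**The remedy has a similar side effect.** A reader might infer that counting users as failures restores the 5.1% error. That is true only if no user would have been pain-free anyway. Otherwise the difference in underlying pain-free rates shrinks in the same way, as the second table shows. The remedy is a choice about what success means; it does not correct the pain score.

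**Using the observed score in ITT, with PP alongside, is coherent.** It is, if stated as the intention. The plan does not state it.

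**The size is assumed.** No painkiller rate is given. The 126 per arm already excludes the expected withdrawals, yet the calculation places users, who should be withdrawn, among those 126. The larger shares are hard to credit: m = 20% means about 22 ban-breakers among 252, all scored exactly 0.

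**Conclusion.** The point holds in a limited form. Following the plan as written, a sore-throat score of 0 recorded at Day 4 after a banned painkiller is a success in the ITT main analysis, and no planned analysis treats painkiller need as a failure.

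The effect is modest and conditional. With equal masking of 5% to 10% of failures in both arms and the truth exactly at the margin, false non-inferiority rises by about 1.3 to 2.8 percentage points (6.39 − 5.13 and 7.96 − 5.13). PP removes most of this but is only the additional analysis.

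The documents do not support the stronger inference that the conclusion will be wrong or biased toward Angal: they give no painkiller rate, and a result near the planned rates would need a net 6 to 9 masked Angal patients to reverse. This is an inexpensive improvement to the plan, not a defect that invalidates it.

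**What to change.** Keep the ban and make two changes.

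1. In Protocol 9.5 and SAP 3.6, state that in the ITT main analysis a patient counts as sore throat present if a painkiller was taken within 12 hours before the Day 4 TSS, or if the patient was withdrawn under 5.3.1, item 11, because one was taken or needed. Use the score as recorded in a sensitivity analysis, and report both.
2. Add one diary line for the name, date and time of any other medicine. Without it the 12-hour rule depends on recall at Visit 2.

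A matching change to LOCF would add little: with no scheduled visits on Days 2 and 3, the last score before a painkiller is usually baseline, when throat pain is an entry condition.

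**Cost.** One added rule, placed in both documents, and one diary line; no extra visits or patients. Users who would have been pain-free anyway become failures, so power falls from 86.5% to between 85.8% and 83.9% if 2% to 10% of successes in both arms are reclassified. The pass rate at the margin for underlying pain-free rates becomes 5.7% to 8.2% over the same range. The text should therefore say that success means pain-free without a painkiller.
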